10.2 CLINICAL LABORATORY PARAMETERS

Descriptive statistics for laboratory values (in US conventional and SI units) and changes from baseline for each assessment time point will be presented for the following laboratory parameters collected in the study including but not limited to the following:

- Hematology: Hb, hematocrit, RBC count, MCV, MCH, MCHC, WBC count, WBC differential, platelet counts and reticulocyte count;
- Chemistry: CPK, ALP, ALT, AST, total bilirubin, LDH, total protein, albumin, glucose, phosphate, BUN, creatinine and potassium;
- Serum iron, ferritin, TIBC, TSAT, and CHr

Laboratory values are clinically significant (CS) if they meet either the low or high CS criteria. The number and percentage of subjects with post-baseline CS values will be tabulated. The percentages are to be calculated relative to the number of subjects with available baseline values and at least one post-baseline assessment. The numerator is the total number of subjects with at least one post-baseline CS value. In addition, shift tables will be presented by time point. The following 2 data listings will be presented by subject:

- A listing of lab values for all lab tests at all collected time points.
- A listing of subjects with post-baseline CS values will be provided including the baseline and post-baseline values.

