3.3. Safety Endpoints

Study-specific safety will be assessed by evaluating the following:

- Incidence of treatment emergent adverse events (TEAEs) and treatment emergent serious adverse events (TESAEs)
- Clinically significant changes in laboratory values from baseline
- Vital signs

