5. STUDY ENROLLMENT AND WITHDRAWAL

5.1. Inclusion Criteria

A subject is eligible for the study if all of the following criteria are met:

- 1. Subject has been informed of the investigational nature of this study and has given written informed consent in accordance with institutional, local, and national guidelines
- 2. Subject is ≥ 18 years of age
- 3. Receiving in-center hemodialysis for end stage renal disease (ESRD)
- 4. Prior ESA use:
 - For a subject converting from an ESA: On ESA ≥6 weeks and the prescribed ESA dose remain stable (as determined by PI) during the 4 weeks prior to initiating roxadustat treatment
 - Subject is initiating anemia treatment: Defined as: < 6 weeks of prior ESA use or no prior ESA use.
- 5. Vascular access must be a functioning native arteriovenous fistula or graft with adequate flow in the opinion of the investigator, or permanent tunneled catheter.
- 6. Screening Hb (based on central lab value; measured within 10 days prior to initiating roxadustat treatment):
 - Subjects converting from an ESA: screening Hb is between 9.0 to 12.0 g/dL
 - Subjects initiating anemia treatment: screening Hb is < 10.0 g/dL
- 7. Ferritin ≥ 50 ng/mL, Transferrin saturation (TSAT) ≥ 10% at screening (subject may qualify after receiving iron supplement per local standard of care)
- 8. Subject's alanine aminotransferase (ALT) and aspartate aminotransferase (AST) are ≤ 3 x upper limit of normal (ULN), and total bilirubin (TBL) is ≤ 1.5 x ULN at screening and prior to initiating roxadustat treatment. TBL up to 2 x ULN may be allowed if AST and ALT are within normal limit)
- 9. Subject's body weight (estimated dry weight in HD subjects) is 45.0 to 160.0 kg

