13.2.2 Repeated or Unscheduled Assessments of Safety Parameters

If a patient has repeated assessments prior to the start of study medication, then the results from the final assessment made prior to the start of study medication will be used as baseline. If EOS assessments are repeated or unscheduled, the last post-baseline assessment will be used as the EOS assessment for generating summary statistics. However, all post-baseline assessments will be used for potentially clinically significant (PCS) value determinations and all assessments will be presented in the data listings.

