13.3 APPENDIX 3: RANGES OF POTENTIALLY CLINICALLY SIGNIFICANT LAB VALUES

Parameter	SI Unit	Lower Limit	Higher Limit
CHEMISTRY			
Alanine Aminotransferase (ALT)	U/L		$\geq 3 * \text{ULN}$
Alkaline Phosphatase	U/L		$\geq 3 * \text{ULN}$
Aspartate Aminotransferase (AST)	U/L		$\geq 3 * \text{ULN}$
Severe liver abnormality			ALT or AST $\geq 3 \times \text{ULN}$ AND Total bilirubin $\geq 2 \times \text{ULN}$
GGT	U/L		$\geq 3 * \text{ULN}$
Calcium	mmol/L	$<0.8 * \text{LLN}$	$>1.2 * \text{ULN}$
Potassium	$\mu\text{mol/L}$	$<0.75 * \text{LLN}$	$>1.2 * \text{ULN}$
Sodium	mmol/L	$<0.9 * \text{LNL}$	$>1.1 * \text{ULN}$
Total Bilirubin	$\mu\text{mol/L}$		$>1.5 * \text{ULN}$
Total Protein	$\mu\text{mol/L}$	$<0.9 * \text{LNL}$	$>1.1 * \text{ULN}$
HEMATOLOGY			
Neutrophils	$10^9/\text{L}$	≤ 1	
Platelet Count	$10^9/\text{L}$	≤ 100	≥ 700
White Blood Cell Count	$10^9/\text{L}$	≤ 2.5	≥ 15
LLN: Lower limit of normal, value provided by the laboratory			
ULN: Upper limit of normal, value provided by the laboratory			

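### The count of clinically significant laboratory values mixes abnormalities present before the first dose with new ones, so on its own it does not measure change from baseline

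*SAP*

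**What the plan says.** Protocol 3.3 lists as a safety endpoint "Clinically significant changes in laboratory values from baseline", and SAP 4.3 repeats it.

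SAP 10.2 sets up the count in three steps:

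- Definition: "Laboratory values are clinically significant (CS) if they meet either the low or high CS criteria". The only such criteria in the SAP are in Appendix 3, titled "RANGES OF POTENTIALLY CLINICALLY SIGNIFICANT LAB VALUES". They are absolute values or multiples of the normal limits, and none refers to the subject's own baseline.
- Numerator: "The numerator is the total number of subjects with at least one post-baseline CS value".
- Denominator: "The percentages are to be calculated relative to the number of subjects with available baseline values and at least one post-baseline assessment". A baseline value must exist, but it need not lie within the limits.

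SAP 13.2.2 adds that "all post-baseline assessments will be used for potentially clinically significant (PCS) value determinations", so repeat and unscheduled results also count.

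SAP 10.2 also plans descriptive statistics of change from baseline, a listing of subjects with post-baseline CS values that shows their baseline values, and shift tables: "In addition, shift tables will be presented by time point". The shift categories are not defined.

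**The concern.** The endpoint is about change, but the count is about level after baseline. A subject whose value is beyond a limit on Day 1 and stays there has not changed, yet enters the numerator. With no control arm, a reader cannot judge from the percentage how much of it was present before treatment.

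The SAP treats adverse events differently. Under SAP 10.1.1 a condition present before the first dose counts as treatment-emergent only if it became more severe. The laboratory count has no matching rule, and no reason is given for the difference. Part of the primary objective is to confirm that the dosing regimens are safe, so the summary of laboratory abnormalities should show which of them are new.

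**Working it through.** **Step 1. Can a subject be CS at entry?** Protocol 5.1 is set against SAP Appendix 3.

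| Parameter | Entry limit | CS limit | CS at entry possible? |
|---|---|---|---|
| ALT, AST | ≤ 3 x ULN | ≥ 3 x ULN | Only at exactly 3 x ULN |
| Severe liver composite | ALT and AST as above; bilirubin above 1.5 x ULN only with normal ALT and AST | ALT or AST ≥ 3 x ULN and bilirubin ≥ 2 x ULN | No: a subject at 3 x ULN for ALT or AST must have bilirubin ≤ 1.5 x ULN |
| Total bilirubin | ≤ 1.5 x ULN, with an exception up to 2 x ULN | > 1.5 x ULN | Yes, between 1.5 and 2 x ULN |
| ALP, GGT | None | ≥ 3 x ULN | Yes |
| Calcium, potassium, sodium, total protein | None | Multiples of LLN and ULN | Yes |
| Neutrophils | None | ≤ 1 x 10^9/L | Yes |
| Platelets | None | ≤ 100 or ≥ 700 x 10^9/L | Yes |
| WBC | None | ≤ 2.5 or ≥ 15 x 10^9/L | Yes |

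The bilirubin exception reads "TBL up to 2 x ULN may be allowed if AST and ALT are within normal limit". Sodium matters only if it is measured: it has a limit in Appendix 3, but Protocol Table 5 does not list it in the chemistry panel.

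**Step 2. Does another output give the missing number?** The number needed is how many subjects without a CS value at baseline had at least one during treatment.

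- Shift tables are produced visit by visit. A subject newly CS at Week 8 and another at Week 16 appear in different tables, and the tables cannot be added up into a count of subjects.
- The listing shows baseline values but gives no rate.
- Change-from-baseline statistics describe the distribution at each visit and do not count subjects.

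**Step 3. How large could the effect be?** The plan states no figure to reproduce, and the documents give no baseline CS rate, so every rate below is an assumption. Let b be the share CS at baseline, q the share of those with a CS value again after baseline, and i the new-onset rate among the rest.

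- Tabulated proportion = b x q + (1 − b) x i
- New-onset proportion among subjects not CS at baseline = i
- Share of the numerator already CS at baseline = b x q / [b x q + (1 − b) x i]

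The simplest case is full persistence (q = 1). The number counted without any change is then 300 x b: 0.02 x 300 = 6 and 0.10 x 300 = 30.

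With N = 300, q = 0.8 and i = 5%:

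| b | Tabulated as planned | New onset, not CS at baseline | Share of numerator already CS |
|---|---|---|---|
| 0% | 0 + 0.05 = 5.00% (15.0 subjects) | 15.0/300 = 5.00% | 0% |
| 2% | 0.016 + 0.049 = 6.50% (19.5) | 14.7/294 = 5.00% | 25% |
| 5% | 0.040 + 0.0475 = 8.75% (26.25) | 14.25/285 = 5.00% | 46% |
| 10% | 0.080 + 0.045 = 12.50% (37.5) | 13.5/270 = 5.00% | 64% |

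Over b from 1% to 10%, q from 0.5 to 1.0 and i from 2% to 5%, the share already CS runs from 9% (b = 1%, q = 0.5, i = 5%) to 85% (b = 10%, q = 1, i = 2%). It is zero if nobody is CS at baseline.

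**The case against.** The case for leaving the plan alone has several parts.

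- **The count is not the only laboratory analysis.** This stands. A reader might infer that baseline values are collected and then ignored. The documents do not support that: baseline enters the change statistics, the shift tables and the listing. It is left out only of the CS count.
- **The table does not claim drug effect.** This also stands. A reader might infer that the SAP presents pre-existing abnormality as having arisen on roxadustat. SAP 10.2 describes the values as post-baseline, states numerator and denominator openly, and does not call them treatment-emergent. SAP 11 says that no hypothesis is tested.
- **The adverse event tables already handle change.** Under Protocol 8.3.7 the investigator judges clinical significance, and clinically significant abnormalities are reported as AEs. These then fall under the new-or-worsened rule of SAP 10.1.1. This helps, but it rests on individual judgement and does not give a rate against the Appendix 3 limits.
- **Entry criteria and the limits keep baseline rates low.** This holds for ALT, AST and the liver composite. Chronic liver disease and active clinically significant infection are excluded, and several limits lie far from normal. How low the rates are for the other parameters cannot be read from the documents.
- **A new-onset count has its own gap.** This stands and shapes the fix. A subject whose bilirubin rose from 1.6 to 5 x ULN would drop out of a count restricted to subjects not CS at baseline, although that too is a change.
- **The table layout may already split by baseline.** SAP 1 places table specifications in a separate document, so this cannot be excluded. The SAP text does not require it.

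**Conclusion.** The point holds in a limited form. Taken alone, the SAP 10.2 count does not measure the stated endpoint, because it includes subjects who met the same Appendix 3 limit before dosing, and no other output specified in the SAP supplies the per-subject rate of new CS values over treatment. It affects bilirubin and the parameters without an entry limit, and is negligible for ALT, AST and the severe liver composite.

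The size is unknown. The 6 to 30 of 300 subjects assumes 2% to 10% already CS, full persistence and planned enrolment as the denominator; the real denominator needs both a baseline and a post-baseline value. It should not be read as a forecast or applied to every parameter. This is a minor point in a descriptive analysis, worth making because the remedy is cheap and loses nothing.

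**What to change.** Add one sentence to SAP 10.2: for each Appendix 3 criterion, the post-baseline CS count will also be tabulated by whether the subject met that criterion, in the same direction, at baseline (the last assessment before the first dose, as SAP 10 defines it). The table would then show:

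- The number and percentage with at least one post-baseline CS value among subjects not CS at baseline, with the same restriction on numerator and denominator.
- The subjects CS at baseline as a separate group, so that worsening in them is not lost.
- The present count of any post-baseline CS value, kept beside these.

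It would help to define the shift-table categories by the same Appendix 3 limits, and to state in SAP 10.2 that those limits are the CS criteria it means.

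The cost is one program filter, one SAP sentence for the split and a slightly longer table. No new data are needed.

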10.3 VITAL SIGNS

Blood pressure and heart rate baselines are defined as the mean of values obtained from the last 6 weeks of screening including Day 1 prior to the first dose. For subjects on hemodialysis, pre-dialysis vital signs will be used. For subjects on peritoneal dialysis, vital signs may be recorded at any time during the visit.

Descriptive statistics for vital signs (e.g., systolic and diastolic blood pressure, MAP, heart rate, respiratory rate and temperature) and their changes from baseline at each visit and at the end of study will be presented.

10.4 COVID-19 POSITIVE PATIENTS

Patients who tested positive for COVID-19 during the study will be recorded on the Adverse Events Form in the eCRF. The following 2 data listings will be presented in COVID-19 positive patients:

- A listing of central lab Hb values with COVID-19 AE start date/stop date, mean Hb before COVID-19 diagnosis, mean Hb after COVID-19 diagnosis.
- A listing of COVID-19 related AEs leading to study drug interruption or withdrawal up to 28 days after last dose.

11 INTERIM ANALYSIS

An interim analysis may be performed to report topline results at the Sponsor's discretion. Since no statistical hypothesis testing is performed for this study, no multiplicity adjustment is required.

For better execution and understanding, certain data points (e.g., data linked to dose adjustments, iron supplementation, etc.) may be analyzed by patients participating under each dialysis organization (i.e., all patients, patients from DaVita, and patients from USRC), as needed.

13 APPENDIX

13.1 APPENDIX 1: SCHEDULE OF ASSESSMENTS

Visit/ Week:	Screening Visit	Day 1	Wk2to8 ± 4 days	Wk 12-24 ^g ± 4days	Post-Treatment ^h or ET ±7 days
Written informed consent	X				
Eligibility criteria	X	X			
Demographics and medical history	X				
Height, weight	X	X ^e			
Blood pressure, heart rate, temperature	X	X	X	X	X
Physical Exam	X			X	
Hemoglobin (central and local)	X ^d		X ^f	X ^f	X ^d
CBC with WBC differential	X	X	Wks4, 8	Wks 16, 24	X
Urinalysis	X	X	Wks4, 8	Wks 16, 24	X
CPK	X	X	Wks 8	Wk 16, 24	
Serum iron, ferritin, TIBC, TSAT, CHr, reticulocytes	X	X	Wk8	Wks 16,24	
HIV ELISA, HBsAg, anti-HCV Ab	X				
Screening hCG pregnancy test	X ^b			Q8Wks	X
Dose adjustment			X	X	
AE/CM recording	X	X	X	X	X
Study drug dispensing		X	X	X	

Ab = antibody; CBC = complete blood count; CHr = reticulocyte hemoglobin content; ELISA = enzyme-linked immunosorbent assay; ET = early termination; HBsAg = hepatitis B surface antigen; hCG = human chorionic gonadotropin; HCV = hepatitis C virus; HIV = human immunodeficiency virus; LFTs = liver function tests; TIBC = total iron binding capacity; TSAT = transferrin saturation; WBC = white blood cells; Wk(s) = week(s);

a Weight only

b Collect from female subjects of child bearing potential only

c Renal ultrasound examination will be performed during screening if no record of a renal imaging modality exists within 24 weeks prior to enrollment.

d Central labs only

e 28 days post last dose of roxadustat

f Collect a separate central Hb only when CBC is not collected

g Week24=EOT

13.2 APPENDIX 2: DATA HANDLING CONVENTIONS

13.2.1 Visit Time Window

Table 5 below presents the visits assigned for efficacy and safety analyses corresponding to the range of treatment days (window) during which an actual visit may have occurred.

Table 5. Analysis Visit Windows

Derived Visit	Scheduled Visit Day ^a	Window
Baseline, Week 0	Day 1	Days \leq 1
Week 2	Day 7*(Week #)+1	Days [Day 2, 21]
Weeks 4-6	Day 7*(Week #)+1	Days [Scheduled Day -7, Scheduled Day + 6]
Week 8	Day 7*(Week #)+1	Days [Scheduled Day -7, Scheduled Day + 13]
Weeks 12-24	Day 7*(Week #)+1	Days [Scheduled Day -14, Scheduled Day +13]
ET ^b	Last assessment between Day 2 and EOT/Week 24 visit day, match to a closest scheduled visit in protocol.	
EOS	Final visit in the Study; For subjects who permanently discontinue roxadustat early or complete the treatment period (24 weeks) but decide not to participate in the extension treatment: around 28 days after the last dose. For subjects who complete the treatment period and decide to participate in the extension treatment: EOT/Week 24 visit day.	

^a: Relative to the first study medication date. For example, Day 1 = the first dose date of study medication.

^b: For patients that are early terminated (ET), the ET visit will be collected on the Week 24/EOT visit eCRF.

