5.4 ADDITIONAL DATA HANDLING RULES AND PRESENTATION SPECIFICATIONS

The following general guidelines will apply to all statistical analyses and data presentations:

- Baseline is defined as the last available value obtained prior to the first dose of study drug, unless otherwise specified in this SAP.
- Hb baseline is defined as the mean of available values obtained during screening prior to the first dose (including pre-dose Day 1 Hb value).

- Baselines for reticulocyte count, reticulocyte hemoglobin content (CHr), serum iron parameters (transferrin, TIBC, TSAT, ferritin, sTfR, and iron) are defined as the values obtained on Day 1 (excluding screening) prior to the first dose.
- Baselines for blood pressure and heart rate are defined as the mean of values obtained during screening (including Day 1) prior to the first dose.
- Unscheduled visits within an allowable window will be grouped into the closest scheduled visits based on the visit window specified in [Appendix 1](#). For subjects who have more than one measurement at a certain scheduled visit, the last measurements will be used, with the exception of CPK, WBC, liver function tests (i.e., ALT, AST, GGT, ALP, and total bilirubin), in which the maximum measurement will be used.
- By default, US conventional units will be used for laboratory value presentations. A separate set of laboratory tables with SI units may be required by regulators, such as the European Medicines Agency (EMA).
- Age is calculated as of date that the informed consent form was signed.
 - age = INTCK('YEAR', Birth date, date of Informed Consent, 'C') where INTCK is a SAS function.
- Duration of treatment or days on treatment is calculated as: last dose date – first dose date +1
- Body weight, height and temperatures will be converted using the following formulas:
 - kg = lb/2.2
 - cm = 2.54 x in
 - C° = (5/9) x (F° – 32)
- Mean Arterial Pressure (MAP) will be calculated for each subject using the following formula: MAP = (2/3) * diastolic blood pressure + (1/3) * systolic blood pressure.
- All percentages will be rounded to one decimal place and lined up by the decimal place. The percentage will be suppressed when the count is zero.
- All tables and listings will have a header showing “FibroGen, Inc.”, the protocol number, and the page number. Footer will indicate the program file path/name, run date and run time.

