10 SAFETY ANALYSES

The safety analysis will be performed using the safety population. Safety parameters include adverse events, laboratory parameters, vital signs, and physical examinations.

For each safety parameter, the last assessment made prior to the first dose of study medication will be used as the baseline for all analyses for that safety parameter.

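### SAP Table 5 gives the end-of-study visit two meanings, so the pooled vital-sign change reported there is neither an on-treatment nor a post-treatment change

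*SAP*

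**What the plan says.** The EOS row of Table 5 in SAP 13.2.1 has two rules. For subjects who go on to the extension, it reads "For subjects who complete the treatment period and decide to participate in the extension treatment: EOT/Week 24 visit day". Early discontinuers share the other rule with completers who "decide not to participate in the extension treatment: around 28 days after the last dose".

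SAP 10.3 says of vital signs that descriptive statistics and "their changes from baseline at each visit and at the end of study will be presented". It makes no split by extension status.

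For laboratory tests, SAP 10.2 asks for "changes from baseline for each assessment time point" and does not name EOS. SAP 13.2.2 does expect EOS summaries: where EOS assessments are repeated or unscheduled, "the last post-baseline assessment will be used as the EOS assessment for generating summary statistics".

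Baseline is stated in two ways. SAP 10 says that for every safety parameter "the last assessment made prior to the first dose of study medication will be used as the baseline for all analyses", and 13.2.2 repeats the last-value rule for repeated pre-dose assessments. SAP 5.4 says "Baselines for blood pressure and heart rate are defined as the mean of values obtained during screening (including Day 1" and pre-dose), and 10.3 agrees with it. SAP 5.4 also uses a mean of pre-dose values for hemoglobin, which 10.2 tabulates as a safety laboratory test.

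**The concern.** A column of a descriptive safety table should describe one state. Here some subjects contribute a reading taken at the end of 24 weeks on roxadustat. The others contribute one taken about four weeks after stopping, when Protocol 4.6 would already have allowed an ESA (from two days after the last dose). The two groups also differ in kind. Everyone entering the extension is a completer, while all early discontinuers, including those who stopped for adverse events (Protocol 5.3), fall in the off-drug group.

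Vital signs are a stated safety endpoint (Protocol 3.3, SAP 4.3). Blood pressure and heart rate are of interest for this drug: Protocol 2.6.1 reports transient heart-rate rises with dose in healthy subjects, Protocol 2.3 lists lack of a hypertensive effect as a potential advantage, and SAP Appendix 7 makes hypertension a specific adverse event. A reader could take the end-of-study change as the on-drug effect or as the effect after washout. It is neither.

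**Working it through.** The plan gives no figure for this point, so there is none to reproduce. The check is of definitions, with three short calculations.

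**1. Are the 28-day values off drug?** Protocol 2.4.1 gives a half-life of 15 to 19 hours in dialysis subjects.
- 28 days: 28 × 24 = 672 h. 672/15 = 44.8 half-lives and 672/19 = 35.4.
- Earliest allowed follow-up, 7 days sooner: 21 × 24 = 504 h, and 504/19 = 26.5 half-lives.

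The values are off drug throughout the visit window.

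**2. Where do the readings fall in time?**
- Week 24 is scheduled on Day 7 × 24 + 1 = 169. Its analysis window is 169 − 14 = 155 to 169 + 13 = 182.
- A completer last dosed on Day 168 or 169 who does not extend has follow-up between Day 168 + 28 − 7 = 189 and Day 169 + 28 + 7 = 204, outside the Week 24 window.
- A subject entering the extension has the same reading under both Week 24 and EOS.
- An early discontinuer last dosed on Day 141 is due on Day 141 + 28 = 169, inside the Week 24 window. Table 5 does not say whether such a reading is kept out. So the Week 24 row does not depend on the EOS definition, but it is not guaranteed to be purely on drug.

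**3. What does the pooled column estimate?** Let f be the share of subjects with an EOS value who enter the extension.

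Pooled change = f × (on-drug change, extenders) + (1 − f) × (off-drug change, the others).

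The on-drug mean over all subjects has the same first term. The difference is therefore (1 − f) × (off-drug change − on-drug change), both taken in the subjects who stop. The documents give neither f nor the changes. Two illustrations, all values assumed, with the same changes in both groups:

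| f | on-drug 5, off-drug 0 | on-drug 0, off-drug 5 |
|---|---|---|
| 0.10 | 0.5 | 4.5 |
| 0.25 | 1.25 | 3.75 |
| 0.50 | 2.5 | 2.5 |
| 0.75 | 3.75 | 1.25 |
| 0.90 | 4.5 | 0.5 |

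In the first case the column understates an on-drug change; in the second it shows one that does not exist on drug.

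**4. How much does the baseline conflict matter?** Take one screening reading S and one Day 1 reading D. The last value is D and the mean is (S + D)/2, so they differ by (D − S)/2, with SD = σ × √2/2 for a within-subject SD of σ. For systolic pressure with σ assumed to be 10, 15 or 20 mmHg:
- Per subject, the SD of the difference is 7.1, 10.6 or 14.1 mmHg.
- For the group mean at the planned n = 300, the SE is 7.07/√300 = 0.41, 10.61/√300 = 0.61 or 14.14/√300 = 0.82 mmHg.
- A drift from screening to Day 1 moves the mean baseline by half its size: 2, 5 or 10 mmHg (assumed) gives 1, 2.5 or 5 mmHg.

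The conflict covers blood pressure (and so mean arterial pressure), heart rate and hemoglobin. For iron and reticulocyte values SAP 5.4 requires Day 1, and Protocol 7.3.1 schedules them on Day 1 before dosing, so the rules differ only if that sample is missing.

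**The case against.** The strongest reply is that the on-treatment change is shown elsewhere. SAP 10.3 presents changes at each visit as well as at end of study, and Week 24 has its own window. That stands: the defect is confined to one column. A reader might infer that the safety changes as a whole cannot be interpreted; the documents do not support that.

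A reader might also infer that the pooling dilutes a true change toward zero by a predictable fraction. That would need a known extension uptake and no change off drug. Neither is documented, and the off-drug group may be on an ESA. Protocol 2.2 names hypertension among the ESA risks, while Protocol 2.3 claims no hypertensive effect for roxadustat, so off-drug readings could be the higher ones.

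On baseline, it is fair to say that the parameter-specific rules in 5.4 and 10.3 agree, that 5.4 allows exceptions to its own general rule, and that a programmer working from 10.3 would use the mean. What remains is that SAP 10 and 13.2.2 carry no exception.

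Stopping main-study data at Week 24 for extension subjects matches the rules for adverse events (SAP 10.1.1) and concomitant medication (SAP 8.2). That explains the first EOS rule but does not justify pooling it with the second. Table specifications sit in a separate document (SAP 1), so a split or footnote may exist there; the SAP itself does not require one.

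**Conclusion.** The point holds for the pooled EOS column. Followed as written, the SAP produces a vital-sign change that mixes on-drug and off-drug readings in proportions set by extension uptake. Its size and direction of error are unknown, and the tabulated illustrations rest wholly on assumed values. Whether laboratory summaries share the problem is less certain, because SAP 10.2 does not name EOS. Nor will every discontinuer have a 28-day value, since Protocol 5.3 asks for that follow-up only where feasible.

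The consequence is limited: the study is descriptive, SAP 11 states that no hypothesis is tested, and the Week 24 summary does not depend on the EOS definition.

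The baseline conflict is a secondary matter of wording. A reader might infer that it too makes the changes uninterpretable, but either definition gives a usable change. With an assumed σ of 10 to 20 mmHg, the group means differ only by chance (SE about 0.4 to 0.8 mmHg at n = 300) unless readings drift between screening and Day 1, and the documents report no such drift.

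**What to change.** In Table 5 and SAP 10.3, replace EOS with two time points:
- **End of treatment:** the last on-treatment value, all subjects.
- **Post-treatment follow-up:** the value about 28 days after the last dose, only for subjects who stopped, with its own n.

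State how on-treatment is bounded relative to the last dose date, and make the EOS selection sentence in 13.2.2 refer to the new time points.

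For baseline, add an exception such as *unless defined otherwise in Section 5.4* to both SAP 10 and SAP 13.2.2. Changing SAP 10 alone would leave the contradiction in 13.2.2.

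The cost is SAP wording and one extra table row. No new data are needed.
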